3.1 Study design

The DYNAMIC RW Phase 1 study is a pragmatic, open-label two-arm parallel-group cluster non-randomized controlled superiority trial implemented in a sequential manner. There are three distinct implementation blocks of half intervention and half control health facilities that will be enrolled in the study at three sequential time points. The intervention consists of the provision to health workers of the ePOCT+ clinical decision support algorithm (CDSA), point-of-care tests proposed by ePOCT+ that are not part of routine care (pulse oximeter, CRP rapid test, additional hemoglobin cuvettes), complementary training on the tool, regular monitoring and mentorship/supervision visits by the study team and/or the District Health Management Team (DHMT). Mentorship and supervision will be enabled by a complementary dashboard (medAL-monitor), used to visualize and monitor study-related indicators.

Since the intervention takes place at the health provider level and their practices are influenced by the context of the health facility they are working in, randomization at health facility level rather than at HCW level or at individual patient level was chosen. The randomization of clusters (i.e. health facilities) will be performed on a 1:1 ratio. Thus, ePOCT+ will be provided to health workers (HWs) of 16 of the 32 selected primary health care facilities (intervention arm) in Rusizi and Nyamasheke districts, while the other 16 health facilities (HFs) will serve as controls (control arm). Sick children aged 1 day to 14 years (inclusive) will be managed in accordance with the study arm to which the HF they attend has been assigned. The comparator for Phase 1 will be routine care as currently implemented in Rwanda supplemented with equivalent clinical training given to the intervention arm. To assess the primary and secondary outcomes, final decision on referral, laboratory test results, diagnoses and treatments at initial consultation will be recorded by HCWs electronically in both arms (in the intervention arm integrated into the CDSA; in the control arm via a simple eCRF without any decision support); children will also be followed-up by a phone call or home visit to their caregiver at day 7 (range 6-14) to determine their clinical status. The study is considered as pragmatic since there are no major exclusion criteria to the population of interest, and the setting and organization of the health facilities remains mostly the same. The trial design is summarized below. Furthermore, in line with the pragmatic nature of the study, the design is adaptive, in that changes in the implementation across the three parallel cluster studies may be made based on monitoring data and feedback from the health facilities. These implementation changes (excluding significant adaptations to algorithm content) will be thoroughly documented and accounted for in comparisons across the three cluster studies.

PHASE 1

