Study design	
The primary intervention study will be conducted using a parallel-group cluster non-randomized controlled superiority trial study design implemented in two phases. Additional mixed-methods operational research will take place throughout the intervention period.
 
Phase 1: parallel cluster randomized controlled study in 32 health facilities
 
The ePOCT+ tool will be introduced sequentially using in three implementation blocks of 10-12 (half intervention and half control) facilities. Each of the parallel cluster study (implementation block) will last for approximately four months, with the first month serving as a phase-in period. The aim is to compare the effect of using ePOCT+ with

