--	---

	
 
- Carbon footprint of the intervention or carbon-saving due to the intervention
 

Procedures and measurements	
Objective 1: Improve integrated management of sick children
 
In Phase 1, eligible HFs will be grouped into three implementation blocks of 10-12 health facilities (half intervention and half control). Randomization will not be done for reasons of feasibility and high chance of contamination if control and intervention facilities are mixed and in close proximity to each other as randomized. Therefore, boundaries between groups of intervention and control facilities will be delineated geographically.
 
Sick children will be enrolled throughout Phase 1, as new blocks of facilities are introduced every four months and control facilities are converted into intervention facilities. Children enrolled in intervention facilities will be managed using ePOCT+, with all data associated with the consultation being captured electronically. Children enrolled in control facilities will be assessed, diagnosed and treated as per routine protocols by clinicians. A similar but simplified tablet or PC application will also be used in control facilities to record only outcome measure related data using an electronic case report form.
 
Primary outcome measure: For measuring antibiotics prescribed at initial consultation, the treatment data recorded in the tablets or PCs by HWs throughout the study will be compared between intervention and control facilities, captured electronically in both facility types.
 
Secondary outcome measure: For assessing clinical cure at day 7, a simple questionnaire (asking if the child is still sick, was hospitalized secondarily, or died) will be administered to all caregivers by phone.
 
In Phase 2, all HFs will be using ePOCT+. Indicators monitored over time and space will be measured the same way as in Phase 1, except that clinical cure, secondary hospitalizations and deaths may not be collected or will be assessed through an automated phone call or SMS sent to caregivers using the same simple questionnaire (resource dependent).
 
Secondary analyses will be used to assess differences in the quality of the consultation made by HWs, including the rational use of antimicrobials (antibiotics and antimalarials). Two sources of data will be used and compared between intervention and control facilities:
 
 
- the final decision on referral, tests performed, final diagnoses retained and treatment prescribed will be recorded in the tablets or PCs by HWs at initial consultations and re-attendance visits.
 
- during a cross-sectional quality of care survey, observers in the consultation room will record key symptoms and signs assessed by HWs, diagnostic tests requested, final decision on referral, final diagnoses retained and treatment prescribed.
 
 
Objective 2: Improve the algorithm and adapt it to spatiotemporal variations
 
In Phase 2 of the study, the algorithm will be improved in terms of diagnostic and prognostic accuracy and adapted to local fluctuations in epidemiology, demography, geography and resource availability. Each potential modification will first be evaluated by the Rwandan clinical expert group for its clinical coherence, safety and potential benefit, and then applied to the retrospective data. If these analyses confirm a clinically relevant positive impact, the change in the algorithm will be implemented in all relevant locations/patient sub-groups and monitored based on the indicators relevant to the specific change in the algorithm collected throughout the study through the tablets.
 
Objective 3: Enhance M&E and supportive supervision
 
Patient-level data will also enhance M&E activities and supportive supervision of the HWs through the medAL-monitor/medAL-outbreak platform. Clinicians will use data generated from their own consultations to self-audit their clinical practices by monitoring quality of care indicators in the medAL-monitor dashboards and improve their skills in specific areas using the e-learning platform. Similarly, members of the DHMT will use medAL-monitor to identify and provide support to HFs in need of additional training and mentorship. In time, this enhanced ability to capacitate HWs and

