3.2 Allocation of health facilities to study arms

The 32 health facilities to be included in the study will be selected from all eligible health facilities in the participating districts (Rusizi and Nyamasheke). Eligible health facilities include public health centers with at least 19 consultations with children between 2 months and 5 years of age per week. Cluster inclusion and exclusion criteria will first be applied to the full list of health facilities in the participating districts prior to selection of the 32 health facilities. Health facilities (or clusters) will be allocated (1:1), to using ePOCT+ (intervention) or routine care (control group). Due to the pragmatic nature of the study, randomization is not possible. Health facilities will be allocated first to one of the three implementation blocks using geographical considerations, and then split into study arms, also using geographical considerations. Similar sample size by study arm and by implementation group will be maintained as much as possible.

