5.4 Baseline characteristics

The baseline cluster (health facility) characteristics that will be summarized by study arm include:

- Number of health facilities by district
- Average number of patients seen per month by health facility
- Availability and readiness of basic health care services score based on the Rwandan Service Provision Assessment (median and IQR)

The baseline patient characteristics that will be summarized by study arm, and for the overall study include:

- Demographics: sex (number and percentage); age (median and IQR), age groups 0-2 months, 2 months - 5 years, 5-14 years (number and percentage)
- Medical history: Main reasons for consultation, history of fever (number and percentage)

Given the pragmatic nature of the study, and so as not to influence the normal management of patients and their outcome in the control arm, clinical signs and comorbidities will not be systematically collected in the control and intervention arm.

Baseline data will be compared across the study arms to confirm no bias due to lack of true randomization.

6. Main analyses

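### SAP 3.1 says facilities will be randomised although arms are set by geography, and SAP 5.4 and 6.1 rely on baseline comparisons and covariates chosen from the data to deal with bias

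*SAP*

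**What the plan says.** SAP 3.1 opens by describing an "open-label two-arm parallel-group cluster non-randomized controlled superiority trial implemented in a sequential manner". Further on, the same section says that "randomization at health facility level rather than at HCW level or at individual patient level was chosen" and adds: "The randomization of clusters (i.e. health facilities) will be performed on a 1:1 ratio". SAP 3.2 then says "Due to the pragmatic nature of the study, randomization is not possible". It explains that facilities go first to one of three blocks by geography "and then split into study arms, also using geographical considerations".

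The protocol is mixed in the same way. The synopsis (Procedures and measurements) says "Randomization will not be done for reasons of feasibility and high chance of contamination", and section 4 calls the design non-randomised. But the synopsis (Study design) carries the heading "Phase 1: parallel cluster randomized controlled study in 32 health facilities", section 5.2 refers to the Phase 1 study as an RCT, and section 13 calls it randomised when setting out how results will be presented.

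On bias, SAP 5.4 says "Baseline data will be compared across the study arms to confirm no bias due to lack of true randomization". SAP 6.1 gives the comparison of baseline characteristics by arm and by cluster study much the same purpose. For the primary model it names age and sex as examples of patient-level covariates. It adds other baseline characteristics where imbalance is found by statistical comparison and by agreement within the analysis team.

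**The concern.** There are three linked problems.

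1. The SAP states a property, randomised clusters, that the allocation it describes does not have. Section 13 of the protocol would carry that label into the presentation of results to the district team, facility staff and communities.
2. A baseline comparison is given a job it cannot do. Similar arms on measured variables do not show absence of bias when neighbouring facilities were placed in the same arm on purpose. Local prescribing habits, supervision and disease mix may be shared within an area and are not measured, or are measured only by proxy.
3. The rule for choosing covariates is applied after the data are seen, by a team working in an open-label trial. The primary estimate then depends in part on choices that were not fixed in advance.

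What is at stake is how strongly a difference in prescribing can be attributed to ePOCT+, and whether the primary model is fully specified.

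**Working it through.** **Labels against allocation.** Every place that describes how facilities reach an arm gives the same account: SAP 3.2 and the synopsis under Procedures and measurements both describe a geographical split. The design statements that open SAP 3.1 and protocol section 4 agree with them. The randomisation wording in the body of SAP 3.1, the synopsis heading, protocol 5.2 and protocol 13 comes with no randomisation procedure. The two accounts cannot both be true, and the non-randomised one is plainly intended.

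**What the baseline table can show.** SAP 5.4 lists, for facilities, the number by district, patient volume and a service-readiness score. For patients it lists sex, age, main reasons for consultation and history of fever. It says that clinical signs and comorbidities are not systematically collected. Pre-intervention antibiotic prescribing, the variable closest to the outcome, is not listed. Study data from a control period come only from groups 2, 4 and 6 (Protocol 8.1.1 and 8.1.6), so there is no matching tablet-based baseline for groups 1, 3 and 5.

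Protocol Table 5 suggests that geography may matter, but not in which direction. For Rusizi against Nyamasheke:

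- Household-survey prevalence over two weeks in under-fives: respiratory infection 14% v 5%, fever 33% v 14%, diarrhoea 24% v 8%.
- HMIS episodes per 1,000 children: cough 612 v 615, diarrhoea 126 v 128, fever 408 v 497.

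The two sources disagree, and the documents do not say how the arms fall across the districts.

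**The plan's own figure.** Inputs from SAP 3.3 are 35% v 26%, two-sided alpha 0.05, 80% power, cluster size 660 and ICC 0.025.

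- Without clustering, the usual two-proportion formula gives 410 per arm.
- Design effect = 1 + (660 − 1) × 0.025 = 17.475.
- Clusters per arm = 410 × 17.475 / 660 = 10.86, rounded up to 11, as stated.
- 16 × 660 = 10,560, consistent with the stated 10,500 per arm.

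Correcting the label changes none of these.

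**Scale of facility variation (illustration only).**

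- SD of a single facility's rate = √(0.025 × 0.35 × 0.65) = 0.0754, or 7.5 percentage points.
- SD of the 16 v 16 arm difference if facilities are exchangeable = 7.54 × √(2/16) = 2.7 points.
- SD if all facilities in a group share one deviation, with three groups per arm (1, 3, 5 v 2, 4, 6; Protocol 4.1) of about equal size = 7.54 × √(2/3) = 6.2 points.
- Midway, with half the variance shared: 7.54 × √(0.5 × 2/3 + 0.5 × 2/16) = 4.7 points.

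The shared fraction is an assumption, because the documents give no geographic correlation. The calculation also takes group deviations as independent. Any part common to both groups of a block cancels in a within-block comparison.

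**What the model does with this.** SAP 6.1 has random effects for facility and patient only. It names no block term, although arms are formed within blocks. If neighbouring facilities share a deviation, the model still treats the 32 facilities as independent, and its interval would not reflect the shared part.

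**The case against.** The strongest reply is that this is an editing slip. The allocation is described consistently, SAP 5.4 itself acknowledges the lack of randomisation, and deleting the stray sentences alters no allocation and no sample size. That is right as far as the label goes. It does not cover the use of baseline data to rule out bias, or the covariate rule.

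A second reply is that the plan has other safeguards, and this also stands:

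- Protocol 4.1 plans the primary comparison within blocks, and longitudinal comparisons of the same facilities between control and intervention periods, giving groups 2 and 4 as examples. The latter are not affected by stable geographic differences. However, they are not the primary analysis and are open to time trends.
- Protocol 4.2.1 repeats facility assessments annually to detect changes that could bias results.
- Protocol 4.2.2 includes a pre-intervention survey round in 18 randomly selected facilities with 25 observed consultations each. The synopsis says that observers record treatment. This covers only a subset and is not in the SAP's baseline list.
- SAP 6.1 does plan adjustment for imbalance, so the baseline table is not the only protection.

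A third reply concerns size. A reader might take the 7.5-point facility SD as the likely bias and set it against the 9-point target. The documents do not support that, because 7.5 points describes one facility, not a difference between arms. Even under the extreme sharing assumption the SD of the arm difference is 6.2 points.

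Finally, adjusting for everything collected is not automatically safe. Main complaint and fever history are recorded after allocation, in different applications in the two arms, so their ascertainment may differ. District may overlap with block or arm.

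**Conclusion.** The concern holds in a bounded form. The randomisation wording in SAP 3.1 and in three places in the protocol is wrong and contradicts the described allocation. Comparing the listed baseline variables cannot confirm absence of bias under geographical allocation without pre-intervention prescribing. Choosing covariates from observed imbalance and by consensus leaves the primary model open in an open-label trial, and block is missing from it.

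A reader might go further and infer that the design as a whole is presented as randomised, or that most of the target effect could be confounding. Neither is supported. The design and allocation statements say non-randomised. The plausible scale runs from an SD of 2.7 points (exchangeable facilities) to 6.2 points (full sharing within each of six groups), against a 9-point target. That range rests on the plan's ICC and control rate and on an assumed degree of sharing. It neither forecasts nor bounds the bias, because geographical allocation does not guarantee exchangeable facilities.

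The sample size is unaffected, and the contamination rationale for geographical allocation is not in question.

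**What to change.** - **Label.** Remove the randomisation wording from SAP 3.1, the synopsis heading, protocol 5.2 and protocol 13. Call the trial non-randomised throughout and describe the geographical allocation once.
- **Baseline comparison.** In SAP 5.4 and 6.1, replace the stated aim of ruling out bias with a description of balance, using standardised differences by arm and by block.
- **Adjustment set.** Fix it before analysis. A workable set is implementation block, age, sex, facility volume and readiness score, with district if it is not collinear with block or arm. Put main complaint and fever history in a sensitivity analysis. Other sets are defensible; what matters is that the set is chosen in advance.
- **Interpretation.** State that residual geographic confounding limits causal conclusions. Bring the within-block and within-facility comparisons from Protocol 4.1 into the SAP as partial safeguards, with the caveat on time trends.

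The cost is wording, one pre-specification decision and a more modest conclusion. With block (2 degrees of freedom) and one each for volume, readiness and district, the cluster-level terms use at most 5 of the 30 left after the intercept and arm with 32 facilities. Allocation, data collection and sample size do not change.

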3.2 Allocation of health facilities to study arms

The 32 health facilities to be included in the study will be selected from all eligible health facilities in the participating districts (Rusizi and Nyamasheke). Eligible health facilities include public health centers with at least 19 consultations with children between 2 months and 5 years of age per week. Cluster inclusion and exclusion criteria will first be applied to the full list of health facilities in the participating districts prior to selection of the 32 health facilities. Health facilities (or clusters) will be allocated (1:1), to using ePOCT+ (intervention) or routine care (control group). Due to the pragmatic nature of the study, randomization is not possible. Health facilities will be allocated first to one of the three implementation blocks using geographical considerations, and then split into study arms, also using geographical considerations. Similar sample size by study arm and by implementation group will be maintained as much as possible.

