3.3 Sample size

The primary analysis will evaluate whether the use of ePOCT+ for case management of sick children in PHC facilities results in decreased antibiotic prescriptions (superiority analysis) at the initial consultation. Superiority in antibiotic prescription is defined as a relative decrease of $\geq 25\%$ in the proportion of children prescribed an antibiotic. We estimated a cluster size of 660 patients (monthly utilization of 220 – accounting for up to 30% non-adherence and/or loss to follow-up from 315 – over 3 months) and an intraclass correlation coefficient of 0.025. Non-adherence here is defined as HWs not using the application for all eligible patients that come to the HF for various reasons. To have 80% power to detect a 25% reduction in antibiotic prescription (from 35% to 26%), for a two-sided hypothesis test at alpha of

0.05, we would require a minimum of 11 clusters per arm. With 16 clusters per arm, over 3 months, we expect a total of 10,500 children in each study arm. Considering the pragmatic/adaptive nature of the study design, if a higher antibiotic prescription in the control arm is encountered (e.g. 45% or higher), each cluster study of 5-6 health facilities per study arm will be sufficiently powered to show a statistically significant reduction in the primary outcome. Sample size calculations were performed in R statistical software (version 4.0.3) using the CRTSize package (Rotondi, 2015).

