6.1 Analysis methods

Analyses will follow CONSORT guidelines (Campbell, Piaggio, Elbourne, & Altman, 2012; Piaggio et al., 2012; Schulz, Altman, & Moher, 2010; Zwarenstein et al., 2008). Outcomes will be described by arm using summary statistics. Baseline characteristics will be compared by study arm and by cluster study to ensure that the pragmatic allocation of health facilities and sequential rollout of the study did not introduce significant bias. Baseline characteristics which will differ between treatment arms within and over all clusters will be described using summary statistics.

Since the documentation of final treatment in both arms is part of the per protocol definition, only the PP population can be used for primary outcome analysis. The primary outcome will be evaluated using a random effects logistic regression model with the binary outcome variable of antibiotic prescription, with study arm and covariates at patient-level (e.g. age, sex) as fixed effects, and cluster (health facility) and patient included as random effects. Binary secondary outcomes will be evaluated in the same way. All estimates will be reported as odds ratios (ORs) with two-sided 95% confidence intervals (CI). The study will be deemed a success if antibiotic prescription at the initial consultation is 25% less in the ePOCT+ arm compared to the control arm, although we expect a greater reduction based on limited pilot data.

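### Arms are assigned in six geographic groups, but the power statement and primary interval treat 32 facilities as independently assigned, so both hold only if areas within a block do not differ in prescribing

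*SAP*

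**What the plan says.** The Protocol synopsis (procedures and measurements) drops randomization and says that "boundaries between groups of intervention and control facilities will be delineated geographically". SAP 3.2 gives the order: facilities are "allocated first to one of the three implementation blocks using geographical considerations, and then split into study arms, also using geographical considerations". Protocol 4.1 names the result. Groups 1, 3 and 5 are intervention, groups 2, 4 and 6 are control, and the primary outcome is compared within blocks (1 with 2, 3 with 4, and so on). With blocks of 10–12 facilities split in half, each group holds five or six facilities.

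The sample size works at facility level. SAP 3.3 states: "We estimated a cluster size of 660 patients", with a single intraclass correlation (ICC) of 0.025. "for a two-sided hypothesis test at alpha of" 0.05, 80% power and 35% v 26%, it says "we would require a minimum of 11 clusters per arm"; 16 per arm are planned. In SAP 6.1 the primary model has arm and patient-level covariates as fixed effects, with "cluster (health facility) and patient included as random effects". Neither document has a term for block, district or allocation group. Protocol 9.2 adds time as a random effect, which does not stand in for area.

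**The concern.** Facilities that receive their arm together, because they lie on the same side of a boundary, are not independently assigned. If prescribing habits, case mix or a local epidemic are shared within an area, that shared part enters the arm contrast. It shrinks with the number of areas per arm, which is three, and not with the number of facilities inside them. A model with independent facility intercepts cannot see it.

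Two statements depend on this: the claim that 11 clusters per arm give 80% power, and the 95% interval behind the primary conclusion. The exposure is greatest for the SAP 3.3 remark that a single block of 5–6 facilities per arm could suffice if control prescribing is 45% or higher. Within one block, one area is set against one area, so area and treatment cannot be told apart.

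**Working it through.** **Inputs.** From SAP 3.3: control 35%, intervention 26%, two-sided alpha 0.05, power 80%, 660 patients per facility (already net of losses), ICC 0.025, 16 facilities per arm. Group sizes of 6, 5 and 5 per arm follow from 16 facilities in three blocks. The share *s* of the ICC that lies between areas within a block is **not in the documents**. It is assumed, over 5–30%.

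**Reproducing the plan's figure.**
- Two-proportion formula, individual allocation: 410 per arm.
- Design effect: 1 + 659 × 0.025 = 17.475.
- Clusters: 410 × 17.475 / 660 = 10.86, rounded up to 11. The SAP figure reproduces, with facilities taken as independent.
- At 16 per arm on the same footing, power is about 93%.

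**Standard error with area variance.** Let v = 0.35 × 0.65 + 0.26 × 0.74 = 0.4199. The variance of the arm difference is

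v × [(1 − 0.025)/(16 × 660) + 0.025(1 − s)/16 + 0.025s × (6² + 5² + 5²)/16²].

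The last factor is 86/256 = 0.336, roughly one third, because there are only three areas per arm.
- s = 0: 0.4199 × (0.0000923 + 0.0015625) = 0.000695, so SE = 0.0264.
- s = 0.10: 0.4199 × (0.0000923 + 0.0014063 + 0.0008398) = 0.000982, so SE = 0.0313.
- s = 0.30: 0.4199 × (0.0000923 + 0.0010938 + 0.0025195) = 0.001556, so SE = 0.0394.

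**Type I error.** Trials were simulated on facility proportions with no arm effect (40,000 per setting) and tested two-sided at 5% with a facility-level t-test. This is a linear stand-in for the SAP's logistic model. Area SD is √(0.025s × 0.35 × 0.65).

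| Share *s* | Area SD (percentage points) | True SE | Ratio to planned SE | Type I error, no block term (as SAP 6.1) | Type I error, block as fixed effect |
|---|---|---|---|---|---|
| 0 | 0 | 0.0264 | 1.00 | 5.0% | 5.0% |
| 5% | 1.7 | 0.0290 | 1.10 | 7.6% | 7.8% |
| 10% | 2.4 | 0.0313 | 1.19 | 10.2% | 10.5% |
| 20% | 3.4 | 0.0356 | 1.35 | 15.4% | 16.8% |
| 30% | 4.1 | 0.0394 | 1.50 | 20.2% | 22.6% |

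**When blocks differ too.** Variation common to both arms of a block cancels from the contrast but still widens an interval that has no block term. With 5% of the variance between areas and 40% between blocks, type I error is 5.2%. With area shares of 10–20%, inflation stayed at about 9–15% in the cases tested.

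**What a group-level analysis can deliver.** Six groups, less three block effects and one arm effect, leave 2 degrees of freedom (critical t 4.30). Simulated power for 35% v 26% is about 44–46% even with no area variance, and falls to 41 / 37 / 31 / 26% at shares of 5 / 10 / 20 / 30%.

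**The case against.** The strongest reply is that the area variance is assumed. If the two areas of a block prescribe alike, the facility-level interval is valid. That stands, and it is why the point is conditional.

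A reader might look to Protocol Table 5 for proof that areas differ: Rusizi v Nyamasheke has under-five fever 33% v 14% and acute respiratory infection 14% v 5%. The table does not support that use. Its HMIS rows show the districts nearly equal for cough (612 v 615) and diarrhea (126 v 128), and reversed for fever (408 v 497). No row measures prescribing, and nothing says that arms follow the district line. A district difference shared by both arms of a block would cancel.

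A reader might also infer that true power falls to about 88–63% over the same range of shares. Those figures belong to a z-test with the area variance known, which no planned or proposed test attains. They should not go into the SAP. Nor do the documents say that each group forms one contiguous territory; only geographic grouping is stated, and that is enough here.

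The plan has partial safeguards: baseline comparison by arm and block (SAP 5.4, 6.1), adjustment for imbalance (SAP 6.1), within-block comparisons, and before–after comparisons in groups 2 and 4 (Protocol 4.1). The last removes a fixed area effect, though not time trends. Adjustment is limited, because SAP 5.4 says that clinical signs and comorbidities will not be collected systematically. Fixed covariates also do not model the correlation that remains within areas.

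Finally, SAP 3.1 says that clusters will be randomized 1:1. If facilities had been randomized one by one, the point would fall. SAP 3.2 and the synopsis say the opposite, and the sections need reconciling.

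**Conclusion.** The point holds as a conditional one and should be fixed. The 11-cluster figure is arithmetically right, but it and the primary interval rest on an unstated assumption: no difference in underlying prescribing between the two areas of a block. A modest departure matters. An area SD of about 2.4 percentage points (10% of the ICC) makes the true SE 1.19 times the planned one and roughly doubles type I error. Over 5–30%, the SE is about 0.029–0.039 and type I error about 8–20% for the model as written.

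These figures illustrate an assumed range and do not estimate what will happen. It would go too far to say that the interval is too narrow whenever areas differ: with a small area share and large between-block variance, the missing block term can offset the inflation almost fully. It would also go too far to say that the trial cannot show an effect.

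**What to change.** 1. In SAP 3.3 and Protocol 9.1, state that 80% power with 11 clusters assumes no area-level variance within blocks. Give the SE and type I error ranges above as an illustration.
2. In SAP 6.1, add block as a fixed effect, in line with the within-block comparison in Protocol 4.1. This does not account for area variance, and it removes the offset described above, so pair it with a pre-specified supporting analysis. That analysis uses the six allocation groups as units within blocks and does not replace the primary model. State in advance that it has about 2 degrees of freedom and under 50% power for 35% v 26%, so a wide interval is not evidence against an effect.
3. Report the three block-specific arm differences with a statement on their consistency. Protocol 4.1 already implies the differences; the consistency statement is new.
4. State in the conclusion that area and treatment cannot be fully separated. Do not let significance of the group-level interval decide how the result is labelled; with no area variance at all, it would miss an effect of the planned size more than half the time.

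The cost is SAP and protocol wording and one extra model, with no new patients or data. The supporting interval will be much wider than the primary one, and the power statement more qualified. The change carries most weight if made before outcome data are seen.
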